7.2.2 Exclusion Criteria: SEQ-HN

A subject may not be enrolled in the noninterventional portion of the study (SEQ-HN), if any of the following exclusion criteria apply:

1. Histologically confirmed salivary gland, thyroid, (primary) cutaneous squamous or nonsquamous histologies (e.g. mucosal melanoma).
2. Concomitant disease or condition that could interfere with the conduct of the study or that would, in the opinion of the investigator, pose an unacceptable risk to the subject in this study.
3. The subject has legal incapacity or limited legal capacity.

7.3 Subject Withdrawal

7.3.1 Removal of Subjects from Treatment or Assessment

Subjects may withdraw their consent to participate in this study at any time without prejudice. The Investigator must withdraw from the study any subject who requests to be withdrawn. A subject's participation in the study may also be discontinued at any time at the discretion of the Investigator and in accordance with his/her clinical judgment. Every effort should be made to complete, whenever possible, the tests and evaluations listed for the End of Treatment visit in AIM-HN subjects. The Sponsor must be notified of all subject withdrawals as soon as possible. The Sponsor also reserves the right to discontinue the study at any time for either clinical research or administrative reasons and to discontinue participation by an individual Investigator or site for poor enrollment or noncompliance.

Overall, the reasons for which the Investigator or Kura Oncology may withdraw a subject from study treatment include, but are not limited to, the following:

- Subject experiences disease progression
- Subject experiences unacceptable toxicity
- Subject experiences toxicity that is deemed by the Investigator to be no longer safe for the subject to continue therapy
- Subject requests to withdraw from the study treatment
- Subject requires medication prohibited by the protocol

- Subject is unwilling or unable to comply with the study requirements
- Subject withdraws consent to collect health information
- Subject was erroneously admitted into the study or does not meet entry criteria
- Subject is lost to follow-up
- Subject becomes pregnant

Subjects enrolled in AIM-HN will return for an End of Treatment visit within approximately 30 days after the last administration of the study drug (or sooner if another anticancer therapy is to be initiated). If a subject fails to return for scheduled visits, a documented effort must be made to determine the reason. If the subject cannot be reached by telephone after 2 attempts, a certified letter should be sent to the subject (or the subject's legally authorized representative, if appropriate) requesting contact with the Investigator. This information should be recorded in the study records.

Prior to enrollment into the study, the Investigator or designee must explain to each subject, that the subject's protected health information obtained during the study may be shared with the study Sponsor, regulatory agencies, and IRB/IEC in order to analyze and evaluate study results. It is the Investigator's (or designee's) responsibility to obtain written permission to use protected health information per country-specific regulations, such as Health Insurance Portability and Accountability Act (HIPAA) in the United States (US), from each subject, or if appropriate, the subject's legally authorized representative. If permission to use protected health information is withdrawn, it is the Investigator's responsibility to obtain a written request, to ensure that no further data will be collected from the subject and the subject will be removed from the study.

7.3.2 Medical Care of Subjects after End of Trial

After a subject has completed the trial or has withdrawn from the study, standard treatment will be administered, if required, in accordance with the trial site's standard of care and generally accepted medical practice and according to the subject's individual medical needs.

7.3.3 Replacement of Subjects

Subject with HRAS mutant HNSCC who are enrolled in KO-TIP-007 and receive a dose of tipifarnib (mITT population for the primary objective) will not be replaced.

SEQ-HN Subjects (HNSCC without HRAS mutations) who are enrolled as part of SEQ-HN and found to have an HRAS mutation following enrollment will be offered participation in AIM-HN (assuming all other eligibility criteria are met). These subjects may be replaced. SEQ-HN subjects (HNSCC without known HRAS mutations) who are enrolled and discontinue participation prior to the collection of outcome data on first line systemic treatment for recurrent or metastatic HNSCC (dates of treatment, performance status, treatment outcome and date of progression) may be replaced.

8 TREATMENT OF SUBJECTS

KO-TIP-007 is a nonrandomized study. Subjects enrolled as part of AIM-HN will receive tipifarnib treatment.

SEQ-HN is noninterventional and used for data collection in control subjects with HNSCC without HRAS mutations. Subjects enrolled in SEQ-HN will not receive tipifarnib treatment and may continue to receive other anticancer therapies and care for their disease according to institutional practice.

The following sub-sections apply only to subjects participating in AIM-HN, the tipifarnib treatment portion of KO-TIP-007.

8.1 Medication

8.1.1 Tipifarnib Administration

[figure not shown]
Tipifarnib will be administered with food at a starting dose of 600 mg, orally, bid on days 1-7 and 15-21 of 28-day treatment cycles.

[figure not shown]
Tipifarnib should be administered orally with a meal, and again with a meal approximately 12 hours later at approximately the same times each treatment day. The interval between administrations should be not less than 8 hours. Subjects should be instructed on the importance of taking their tipifarnib dose with a meal as the presence of food has been shown to improve the absorption of tipifarnib, as well as to reduce variability in the pharmacokinetic profile.

[figure not shown]
Tablets should be swallowed whole with water (~8 oz. or 250 mL). Tablets may be chewed or crushed if the Investigator deems it necessary. Use of a percutaneous endoscopic gastrostomy tube or nasogastric tube is allowed at the judgment of the Investigator.

[figure not shown]
If a dose is vomited or partially vomited it should not be replaced with a new dose. Dosing should resume at the next scheduled dose time.

[figure not shown]
The first study dosing (Cycle 1 Day 1) will take place in the study clinic. On Cycle 1 Day 1, the investigator will provide tipifarnib to the subject from bulk supplies. Subjects will be provided with diaries with instructions to record the date and time of each dose and asked to bring the diaries and tablet bottles to each clinic visit for subject compliance and drug accountability review by the site staff.

8.1.3 Treatment of Tipifarnib Overdose

An overdose is defined as any dose greater than 20% over the daily intended tipifarnib dose. Any overdose must be recorded in the trial medication and AE sections of the eCRF. There is no known antidote for tipifarnib. In the event of overdose of tipifarnib, subjects should receive appropriate advice and supportive medical care by the Investigator or his/her designee and be followed-up accordingly.

For monitoring purposes, any case of overdose – whether or not associated with an AE (serious or non-serious) – must be reported to the Sponsor in an expedited manner.

8.1.4 Prior and Concomitant Medications

All prescription and over-the-counter medications taken by a subject within 28 days before the first study drug administration will be recorded in the eCRF. In particular, subjects will be asked about the use of agents that may affect the mevalonate pathway including statins (e.g. atorvastatin, rosuvastatin, pravastatin), bisphosphonates (e.g. pamidronate, risedronate, ibandronate, etidronate, alendronate) and nutritional agents (e.g. coenzyme Q₁₀, ubiquinone).

Supportive care medications, e.g. transfusions, growth factors or intravenous hydration, considered necessary for the subject's safety and well-being may be given at the discretion of the Investigator. Any additional concomitant therapy that becomes necessary during the trial and any

change to concomitant drugs must be recorded in the corresponding section of the eCRF, noting the name, dose, duration, and indication of each drug.

BSC will be provided by the clinical study sites according to local guidelines and standard practices.

Furthermore, the following treatments are allowed during the trial:

- Correction of electrolyte deficiency.
- Radiotherapy for pain control against non-target lesions as long as it is not anticipated to influence bone marrow function.
- Total tumor resection in responding subjects who have become candidates for curative resection.
- Hematopoietic growth factors and transfusions of blood or blood products in subjects who are experiencing hematological toxicity in accordance with standard institutional practice. However, such supportive care should not be used prior to hematological findings unless absolutely clinically necessary and after discussion with the Sponsor or designee's medical monitor.
- Antiemetic therapy in a subject experiencing gastrointestinal symptoms in accordance with standard clinical practice. If a subject experiences vomiting or nausea, prophylactic antiemetic medications may be administered with subsequent treatment in accordance with standard clinical practice.
- Concurrent use of adjuvant hormonal therapy for breast cancer or hormonal treatment for castration sensitive prostate cancer.

8.1.5 Non-permitted Treatments

Use of the following medications and therapies is not allowed during the trial in subjects participating in AIM-HN:

- Investigational agents other than tipifarnib.
- Any other anticancer therapy, including radiation or surgery, for the primary disease under study with the exception of palliative treatment of non-target lesions or treatment of residual disease in study subjects who have experienced a partial response during the study.
- High dose systemic corticosteroids or any other immunosuppressive drugs except:
 - Systemic glucocorticosteroid treatment administered with a daily dose of ≤ 20 mg prednisone or equivalent,
 - Single doses for the management of treatment-related AEs or for premedication of BSC agents.

- Short course (≤ 7 days, including tapering) high dose systemic steroids for the treatment of upper airway obstruction associated with HNSCC
- Strong inhibitors or inducers of CYP3A4 or UGT beginning at least 14 days prior to Cycle 1 Day 1 and during the subject's participation in the tipifarnib treatment portion of this study. See [Appendix III \(Table 12\)](#) for a list of medications classified as strong inhibitors or inducers of CYP3A4. If continued concomitant therapy is needed, subjects should be transitioned to a medicine that is not a strong inhibitor or inducer of CYP3A4 or UGT.
- Sensitive substrates of CYP3A4 beginning Cycle 1 Day 1 and during the subject's participation in the tipifarnib treatment portion of this study. See [Appendix III \(Table 12\)](#) for a list of medications classified as sensitive CYP3A4 substrates. If continued concomitant therapy is needed, subjects should be transitioned to a medicine that is not a sensitive substrate of CYP3A4.
- Enzyme-inducing anti-convulsants (e.g. phenytoin, phenobarbital, and carbamazepine) beginning at Cycle 1 Day 1 and during the subject's participation in the tipifarnib treatment portion of this study. If needed, subjects may use non-enzyme-inducing anti-convulsants (e.g. gabapentin, topiramate, valproate) while taking tipifarnib.

If the administration of a non-permitted concomitant drug becomes necessary during the trial, e.g., because of AEs or disease progression, the subject in question will be withdrawn from the trial, and the subject's data which will have been obtained before the withdrawal may be used for safety and efficacy evaluations.

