Tumor assessment for the primary analysis will be performed by the IRF according to RECIST v1.1 and assessed by an Independent Data Monitoring Board (IDMB). Investigator assessment of tumor response will also be collected and reported as a supportive analysis. Assessments will be performed at screening and approximately every 8 weeks for the first 12 months of a subject's participation in AIM-HN; thereafter, tumor response assessment should occur approximately every 12 weeks until disease progression. Radiological assessments will be discontinued at the time of tumor progression. If the subject initiates a new anticancer therapy without evidence of disease progression by RECIST v1.1, tumor scans should continue until there is evidence of disease progression unless withdrawal of subject's consent to study procedures. Local investigator evaluation of tumor assessment will guide on-study treatment decisions, including decisions to stop study treatment due to progressive disease.

Upon disease progression, all subjects will be followed approximately every 12 weeks for survival and the use of subsequent therapy until either death or End of Study (up to 2 years since the enrollment of the last study subject in AIM-HN, see [Section 6.7.1](#)), whichever occurs first.

All subjects will be followed-up for safety through the End of Treatment visit which occurs approximately 30 days after treatment discontinuation or until immediately before the administration of another anticancer treatment, whichever occurs first. Additional safety follow-up may be conducted if unresolved toxicity is present at this End of Treatment visit. The IDMB will provide periodic evaluations of safety and other data to ensure adequate benefit/risk as well as the validity and scientific merit of the study.

An overview of the AIM-HN design is shown in [Figure 2](#).

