9.2.8 Follow up Visit

Follow up visit(s) are required only for subjects who terminated treatment for reasons other than disease progression and should occur approximately every 8 or 12 weeks (± 5 days) until disease progression. If the subject initiates a new anticancer therapy without evidence of disease progression by RECIST v1.1 criteria, tumor assessments should continue until there is evidence of disease progression unless withdrawal of subject's consent to study procedures.

The assessments to be conducted at these visits are:

- Ascertainment of details of any new anti-cancer treatments/surgeries (name, dates (start, end), treatment outcome (response and response criteria), duration of response)
- Radiographic Imaging: to be performed if not done within the prior 8 weeks or if a tumor assessment is required for the confirmation of response.
 - CT scan with a contrast agent is the preferred imaging method and the same technique should be used at baseline and post-treatment assessments. CT scan coverage should encompass scans of the neck (including the skull base), chest and abdomen (including the liver and adrenals). Any other areas of disease involvement should be scanned based on the subject's signs and symptoms.
 - Transfer of tumor scans and related clinical information to IRF

- Assessments of AEs and concomitant medications may also be conducted if AEs were not resolved at the time of the End of Treatment visit.

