10.1.2 Method and Timing

Radiological assessments of the tumor lesions will be made at screening (within 4 weeks prior to first study drug administration on Cycle 1 Day 1) and at least once approximately every 8 weeks (± 5 days) for 12 months, thereafter once approximately every 12 weeks (± 5 days). Additional tumor assessments may be conducted at the judgment of the Investigator.

Radiological assessments will be discontinued at the time of tumor progression. Subjects who discontinue treatment for reasons other than disease progression must continue tumor assessments until disease progression. Collection of response data may continue upon initiation of another anticancer therapy unless the subject withdraws their consent to study procedures.

Radiological assessments may also be conducted at treatment discontinuation (End of Treatment visit) if the reason for the treatment termination is other than disease progression and a tumor assessment was not done within 8 weeks before treatment discontinuation (assessment must be conducted before subsequent anti-tumor therapy is started). Scans at the End of Treatment visit will be also conducted if required to confirm response to treatment.

[figure not shown]
Lesions to be included in the tumor assessments should follow RECIST v1.1 (See [Appendix I](#)). CT scan with a contrast agent is the preferred imaging method and the same technique should be used at screening and post-treatment assessments. CT scan coverage at screening should encompass scans of the neck (including the skull base), chest and abdomen (including the liver and adrenals). Any other areas of disease involvement should be scanned based on the subject's signs and symptoms.

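### Protocol 8.1.5 takes a subject who needs a non-permitted drug out of the trial, while 7.3.1 and the follow-up sections stop treatment only; read literally, 8.1.5 can lose outcomes for prognosis-related reasons, mainly overall survival

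*Protocol*

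**What the plan says.** Protocol 8.1.5 lists what AIM-HN subjects may not receive. The list includes other anticancer therapy (with limited exceptions), higher-dose systemic steroids outside three exceptions, strong CYP3A4 or UGT inhibitors and inducers, sensitive CYP3A4 substrates and enzyme-inducing anticonvulsants. The section closes with a rule: "If the administration of a non-permitted concomitant drug becomes necessary during the trial, e.g., because of AEs or disease progression", then "the subject in question will be withdrawn from the trial". The subject's "data which will have been obtained before the withdrawal may be used for safety and efficacy evaluations".

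Protocol 7.3.1 names the same event, "Subject requires medication prohibited by the protocol", but in a list of reasons for which the investigator or sponsor "may withdraw a subject from study treatment include, but are not limited to, the following".

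Other sections keep data collection going after treatment stops:

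- 10.1.2: "Subjects who discontinue treatment for reasons other than disease progression must continue tumor assessments until disease progression".
- 9.2.8 (and 6.2.1 in similar terms), for subjects who start new anticancer therapy without progression: "tumor assessments should continue until there is evidence of disease progression", unless consent to study procedures is withdrawn.
- 6.2.1 and 6.6: "Upon disease progression, all subjects will be followed approximately every 12 weeks for survival and the use of subsequent therapy", until death or End of Study.
- 9.2.9: survival contact starts at progression or at withdrawal of consent for further procedures.

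In the SAP, OS is censored at the date last known alive (7.3.5). PFS is censored under Table 1, and DOR uses the same rules (7.3.3).

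**The concern.** The two withdrawal rules share a trigger but differ in scope. One ends trial participation; the other ends treatment. A site cannot both take a subject out of the trial under 8.1.5 and carry on the follow-up that 10.1.2 makes mandatory.

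The triggers that 8.1.5 gives as examples, adverse events and progression, are plausibly linked to prognosis. If follow-up ends there, Kaplan-Meier treats the subject as having the same later risk as those still followed. Where the true risk is higher, survival is overstated. AIM-HN has a single arm, so there is no comparator in which such a bias could partly cancel.

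**Working it through.** **Step 1. Is trial just a loose word for treatment?** Protocol 6.6 and SAP 5.1 both refer to criteria for withdrawal from the trial or from treatment, as two things. Section 8.1.5 also mentions only earlier data, and makes their use optional, whereas 12.5 says that no data will be excluded. The literal reading is therefore open to a site.

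**Step 2. Does survival contact catch these subjects?** The triggers in 9.2.9 are progression and withdrawal of consent for procedures. A subject withdrawn under 8.1.5 before progression, with consent intact, meets neither. That subject could be followed less than one who withdrew consent to procedures.

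**Step 3. Which endpoints are exposed?**

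- *OS (other secondary, descriptive).* Deaths after an 8.1.5 withdrawal would be missed, and the subject censored at the date last known alive.
- *PFS and DOR, anticancer drug.* Little is added. If progression has occurred, the event has normally been counted. If not, SAP Table 1 censors at the last adequate assessment before the new therapy whether or not scans continue, and Protocol 12.1.1 also censors DOR at that point.
- *PFS and DOR, other prohibited drug.* Later progressions would be lost. SAP Table 1 has no row for a protocol-mandated withdrawal; the nearest rows (no progression and no death reported, or lost to follow-up or consent withdrawn) censor at the last adequate assessment. The rule that counts a death within two scan intervals as an event works only if the death is captured.
- *Objective response rate (ORR, primary).* Protocol 12.2.1 classes missing response as failure, so a lost confirmatory scan can only lower the rate.

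**Step 4. How large could the OS effect be?** The plan states no figure to reproduce, so this is an illustration.

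From the documents: median OS of 5 to 8 months in second line (Protocol 4.3) and at least 80 AIM-HN subjects (Protocol 6.2.1).

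Assumed: exponential survival; a share w needs a prohibited drug at a time spread evenly over months 0 to 6; the hazard is multiplied by h from then on.

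Let λ = ln 2 / median and k = (h − 1)λ.

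- With censoring at withdrawal, Kaplan-Meier sees only hazard λ, so S_KM(12) = e^(−12λ). This is 18.9% for a median of 5 months and 35.4% for 8 months.
- With full follow-up, S(12) = e^(−12λ) × [(1 − w) + w f], where f = (e^(−6k) − e^(−12k)) / (6k).
- Example, median 5, w = 10%, h = 2: λ = k = 0.1386 and f = (0.4353 − 0.1895) / 0.8318 = 0.2955. S(12) = 0.1895 × (0.9 + 0.02955) = 17.6%. The overstatement is 18.9 − 17.6 = 1.3 points.

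| Median OS | w | h | Full follow-up | Censored | Overstatement (points) |
|---|---|---|---|---|---|
| 5 | 10% | 2 | 17.6% | 18.9% | 1.3 |
| 5 | 10% | 3 | 17.2% | 18.9% | 1.7 |
| 5 | 20% | 2 | 16.3% | 18.9% | 2.7 |
| 5 | 20% | 3 | 15.5% | 18.9% | 3.4 |
| 8 | 10% | 2 | 33.5% | 35.4% | 1.9 |
| 8 | 10% | 3 | 32.6% | 35.4% | 2.8 |
| 8 | 20% | 2 | 31.6% | 35.4% | 3.8 |
| 8 | 20% | 3 | 29.8% | 35.4% | 5.5 |

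Overstatements use unrounded values. With h = 1 the bias is zero in every row. A simulation under the same assumptions agrees to within about 0.2 points.

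The number of 80 subjects whose later survival would be lost is 80 w (1 − e^(−6λ)) / (6λ). That is 5.4 and 10.9 for median 5 (w = 10% and 20%), and 6.2 and 12.5 for median 8.

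For scale, the standard error of 12-month OS with 80 fully followed subjects is √(0.189 × 0.811 / 80) = 4.4 points, or √(0.354 × 0.646 / 80) = 5.3 points. Most of these biases are smaller than that, but no confidence interval would reflect them.

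**The case against.** The strongest reply is that the rest of the protocol makes the intent plain. Sections 6.2.1, 6.6 and 9.2.9 schedule survival contact after progression and record subsequent therapy, so the protocol cannot sensibly be read as ending follow-up whenever such therapy begins. Section 8.1.5 ties several of its bans to the tipifarnib treatment portion of the study, which suggests that trial was used loosely. It also does not forbid later data collection.

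Much of this stands. A reader might infer that every subject given post-progression therapy is lost to OS, with a far larger bias. The documents do not support that, because follow-up of exactly those subjects is written out explicitly. A reader might also infer that PFS and DOR are biased upward across the board, or that ORR is inflated. Step 3 shows that neither follows.

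It is also fair that the affected group may be small. For CYP3A4 and UGT agents and for anticonvulsants, 8.1.5 points to alternatives, and it exempts some steroid use.

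The reply does not remove the conflict. Sections 8.1.5 and 7.3.1 still give different consequences for one trigger. A subject withdrawn before progression still falls between the triggers in 9.2.9, and the SAP has no rule for the case.

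**Conclusion.** The inconsistency is real and should be corrected. It is a conflict of wording with a possible effect on secondary endpoints, chiefly OS, and to a lesser extent PFS and DOR (DOR is a key secondary endpoint) when the drug is not an anticancer therapy. It does not threaten the primary ORR.

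The size cannot be derived from the documents. The range of 1.3 to 5.5 points in 12-month OS rests on assumed shares, timing and hazard ratios, and on sites following 8.1.5 literally. It falls to zero if withdrawal is unrelated to prognosis or if sites kept following these subjects.

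**What to change.** **Protocol.** Reconcile 8.1.5 with 6.2.1, 6.6, 7.3.1, 9.2.8, 9.2.9 and 10.1.2 so that the end of study treatment is distinct from the end of data collection. The tumour and survival follow-up already scheduled would continue unless consent for that follow-up is withdrawn. This takes no view on which drugs are prohibited or when treatment stops.

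**SAP.** State how a subject withdrawn under 8.1.5 is handled for OS, PFS and DOR, either as a named row in Table 1 or by reference to an existing one. Report how many there were, with the trigger and timing. Because SAP section 3 records early closure of the study, also retrieve vital status, where permitted, for any subject already withdrawn this way.

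**Cost.** One protocol sentence or a site letter, a few lines in the SAP and a short listing. No new visits are needed. Retrieval takes some site effort, and survival data not retrieved may be unrecoverable later.
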